6 STATISTICAL ANALYSES

6.1 Primary Endpoints

The primary endpoint for the dose escalation phase is the incidence of dose-limiting toxicities (DLTs).

AEs that meet the criteria for a DLT will be denoted in the overall AE listing.

6.2 Secondary Endpoints

Cell kinetics data profiles will be presented in a data listing based on the CK Analysis Set.

Response is assessed by the investigators per the response criteria defined in Appendix 4 in the protocol, with status and date at each assessment recorded on the “Disease Response Assessment” CRF. Disease response data will be presented in a data listing based on the Safety Analysis Set.

6.3 Exploratory Endpoints

6.3.1 Adeno-associated Virus

Presence of adenovirus vector in blood and urine data will be assessed. Results will be presented in a data listing based on the Safety Analysis Set.

6.3.2 Biomarkers

Biomarker data will be summarized based on the Safety Analysis Set.

Individual levels of circulating cytokines at baseline and post drug administration will be presented in a data listing. Graphical representation of individual cytokine-time profile will be provided.

6.4 Baseline and Other Summaries and Analyses

6.4.1 Baseline Summaries

6.4.1.1 Demographic Characteristics

The following demographic and baseline characteristics will be summarized by number and percentage based on the Safety Analysis Set:

- Sex (Female, Male, Undifferentiated, Unknown)
- Race (White or Caucasian, Black or African American, Asian, American Indian or Alaska Native, Native Hawaiian or other Pacific Islander, Not Reported, Unknown)
- Ethnicity (Hispanic or Latino, Not Hispanic or Latino, Not reported, Unknown)

Age at Screening (years), height (cm), weight (kg), body mass index (BMI) (kg/m^2) will be summarized with descriptive statistics.

In addition, a data listing will be created based on the FAS.

6.4.1.2 Baseline Disease Characteristics

The following baseline disease characteristics will be summarized by number and percentage based on the data collected on the “AML History” and “ECOG Assessment” eCRF. The summary will be based on the Safety Analysis Set.

- Original WHO diagnosis
- AML Risk category (Favorable/Intermediate/Adverse)
- Presence of extramedullary disease (Yes/No/Unknown)
- History of GvHD (Yes/No)
- Type of GvHD (Acute/Chronic/Overlap)
- Last maximum grade of GvHD (Grade 1/2/3/4)
- ECOG performance status at baseline

In addition, a data listing will be created based on the FAS.

6.4.2 Study Conduct and Subject Disposition

6.4.2.1 Disposition

The percentages below will be calculated based on the number of subjects treated and summarized as follows:

- Number of subjects enrolled, those who received leukapheresis, and those who were treated
- Number (%) of subjects who completed the study (ie, followed for 112 weeks)
- Number (%) of subjects who discontinued the study prior to Week 112 visit, overall and by the main reason for discontinuation of the study

Duration of follow-up will be presented in a data listing based on the Safety Analysis Set. It is calculated as follows:

$$\text{Duration of follow up (months)} = (\text{Last date the subject is known to be alive} - \text{Date of study drug infusion} + 1) / 30.4375$$

6.4.2.2 Protocol Deviations

Potentially important protocol deviations will be identified prior to database lock and will be presented in a data listing based on the Safety Analysis Set.

6.4.3 Extent of Exposure

Exposure will be presented based on the Safety Analysis Set.

6.4.3.1 NTLA-5001 Product

Data recorded on the “NTLA-5001 Dosing” eCRF including assigned dose level, infusion start date/time, stop date/time and reason for infusion alteration will be provided in a data listing for subjects who received NTLA-5001 infusion.

6.4.3.2 Lymphodepleting Chemotherapy

Lymphodepleting chemotherapy may be administered in the inpatient or outpatient setting for up to 3 consecutive days (Day -5, Day -4, and Day -3) at 24-hour (\pm 3 hours) intervals. Data recorded on the “Lymphodepleting Chemotherapy” eCRF will be provided in a data listing including the following information:

- Type of lymphodepleting chemotherapy
- Start and end date
- Dose administered (unit)
- Body surface area (m²)

6.5 Safety Summaries and Analyses

All safety analyses will be based on the Safety Analysis Set. All safety data that occurred during the safety reporting period as defined in Section 5.4 will be listed.

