9.4 Statistical Analyses

This section is a summary of the planned statistical analyses. The statistical analysis plan will include a more technical and detailed description of the statistical analyses described in this section. CK, CK/PD, and immunogenicity analysis plans will be described in separate document(s).

Descriptive statistics, including 'n', mean standard deviation and/or standard error, median, range, and geometric mean for numerical variables (as applicable), and frequency and percentages for categorical variables, will be presented.

The Safety Analysis Set (SAS) will be used for all clinical data summaries of safety and tolerability. The Efficacy Evaluable Set will be used for all disease assessment related efficacy analysis.

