4 ANALYSIS SETS

For purposes of analysis, the following analysis sets are defined in [Table 2](#).

Table 2 **Analysis Sets**

Population	Description
Enrolled Set	All subjects who meet all inclusion/exclusion criteria
DLT Evaluable Set	All subjects who receive NTLA-5001 and either experience DLT(s) regardless of whether a full dose was administered or receive the full assigned dose without DLTs and complete Day 29 assessments. Subjects without DLTs who do not receive the full dose of NTLA-5001 as per their assigned dose cohort or did not complete Day 29 assessments are not evaluable for DLTs.
Full Analysis Set (FAS)	All subjects who undergo leukapheresis
Safety Analysis Set	All subjects who receive NTLA-5001
Cell Kinetics (CK) Analysis Set	All subjects who receive NTLA-5001 and have at least one evaluable CK sample

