5 GENERAL METHODOLOGY AND CONVENTIONS

Qualitative/categorical data will be summarized by frequency counts and percentages. Unless otherwise specified, the calculation of proportions will be based on the sample size of the population of interest. Counts of missing observations will be included in the denominator and presented as a separate category.

Continuous variables will be summarized using descriptive statistics ie, number of non-missing values and number of missing values [ie, n (missing)], mean, median, standard deviation, minimum, maximum and first and third quartile (Q1 and Q3).

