6.5.1 Adverse Events

An AE is considered a treatment emergent adverse event (TEAE) if the event started or worsened during the safety reporting period as defined in Section 5.4.

All analyses will be based on TEAE unless otherwise specified. The AE listings will include all AEs (whether treatment-emergent or not).

AEs will be coded using the current version (as of study start) of MedDRA. Severity of AEs will be assessed by the Investigator using the National Cancer Institute (NCI) Common Terminology Criteria for Adverse Events (CTCAE), Version 5.0 toxicity grading criteria except CRS and ICANS, which will be graded by the Investigator according to the ASTCT criteria (1).

An event will be considered treatment related if the investigator considered the event related to the study drug, ie, relationship to NTLA-5001 = “Possible” or “Probable”, or if relationship is missing.

For summaries by System Organ Class (SOC) and preferred term (PT), each subject will be counted once per SOC and once per PT. In the summary of TEAEs by toxicity grade, subjects will be counted once at the highest severity reported at each level of summarization.

A high-level summary of AEs will include the number and percent of subjects with:

- Any TEAEs
- DLTs
- Treatment-related TEAEs
- Serious TEAEs
- Treatment-related serious TEAEs
- Grade ≥ 3 TEAEs
- Grade 3
- Grade 4
- Grade 5
- Treatment-related Grade ≥ 3 TEAEs
- Grade 3
- Grade 4
- Grade 5
- TEAEs leading to study drug infusion interruption
- Treatment-related TEAEs leading to study drug infusion interruption
- TEAEs leading to study drug infusion discontinuation
- Treatment-related TEAEs leading to study drug infusion discontinuation
- Treatment emergent AEs of special interest (AESIs)
- Treatment-related treatment emergent AESIs
- TEAEs leading to death
- Treatment-related TEAEs leading to death

The AESIs are defined in Section 8.5 in the protocol and will be summarized based on the data collected on the “Adverse Events” eCRF.

Adverse Events by Preferred Term

The following summaries will be provided by preferred term only by decreasing frequency.

- TEAEs by PT (all causality)
- Serious TEAEs by PT (all causality)
- Non-serious TEAEs by PT (all causality)

All AE data will be presented in a data listing.

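### The only planned DLT percentage, for the escalation primary endpoint, is taken over all treated subjects, while the DLT Evaluable Set is defined but used in no analysis

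*SAP*

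**What the plan says.** SAP 6.1 names DLT incidence as the primary endpoint of the escalation phase. The only output it then plans is a flag: "AEs that meet the criteria for a DLT will be denoted in the overall AE listing". It gives neither a rate nor an analysis set.

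The only planned count and percentage is in SAP 6.5.1, where DLTs are the second item of a list introduced by "A high-level summary of AEs will include the number and percent of subjects with". Two rules set the denominator of that row:

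- SAP 6.5: "All safety analyses will be based on the Safety Analysis Set".
- SAP 5: unless otherwise specified, "the calculation of proportions will be based on the sample size of the population of interest".

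SAP Table 2 defines the Safety Analysis Set as all subjects who receive NTLA-5001. It defines the DLT Evaluable Set more narrowly, as treated subjects who "either experience DLT(s) regardless of whether a full dose was administered or receive the full assigned dose without DLTs and complete Day 29 assessments". Those without a DLT who did not receive the full assigned dose, "or did not complete Day 29 assessments are not evaluable for DLTs".

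Protocol 9.4 takes the same line as SAP 6.5: "The Safety Analysis Set (SAS) will be used for all clinical data summaries of safety and tolerability". Protocol Table 9-1 also defines a DLT Evaluable Set, and the protocol likewise gives it no analysis.

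**The concern.** An incidence needs a denominator of subjects in whom the event could have been observed. The SAP defines that group and then reports the primary endpoint on a wider one. A subject who had no DLT but received a partial infusion, or left before completing Day 29, adds to the denominator without giving full information about DLTs. The percentage is pulled toward zero, and a row showing 0% does not reveal how many subjects were actually evaluable.

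The omission looks like an oversight. The other sets in SAP Table 2 are put to use: the Safety Analysis Set throughout, the Cell Kinetics set in 6.2, the Full Analysis Set for listings in 6.4.1, and enrolled counts in 6.4.2.1. The SAP even extended the protocol's sentence on non-evaluability by adding the Day 29 condition. SAP 7 records that the Efficacy Evaluable Set was dropped but does not mention the DLT Evaluable Set.

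**Working it through.** **Planned size.** The only stated count tied to evaluability is in SAP 3.2: up to 36 evaluable subjects in escalation. It reproduces: 2 arms × 3 cohorts × 6 = 36. Adding 2 × 9 = 18 for expansion gives 54. There is no hypothesis or formal sample size calculation, so no power formula applies.

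**Inputs.** Two subjects received NTLA-5001 before the sponsor terminated the study (SAP 7). Set definitions are from SAP Table 2, and the denominator rules are from SAP 5 and 6.5.

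**Relation between the two rates.** Any treated subject with a DLT is in the DLT Evaluable Set by definition and in the Safety Analysis Set because treated. With k subjects having a DLT, the numerator is k in both sets. Provided at least one subject is evaluable:

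Safety Set % = evaluable % × (evaluable N / treated N)

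The ratio cannot exceed 1, so the planned percentage equals or understates the evaluable rate.

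**All possibilities with 2 treated subjects.** Let D = DLT, E = evaluable without DLT, N = not evaluable and without DLT.

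| Pair | Safety Analysis Set | DLT Evaluable Set | Same N? | Same %? |
|---|---|---|---|---|
| D, D | 2/2 = 100% | 2/2 = 100% | yes | yes |
| D, E | 1/2 = 50% | 1/2 = 50% | yes | yes |
| D, N | 1/2 = 50% | 1/1 = 100% | no | no |
| E, E | 0/2 = 0% | 0/2 = 0% | yes | yes |
| E, N | 0/2 = 0% | 0/1 = 0% | no | yes |
| N, N | 0/2 = 0% | 0/0, not estimable | no | no |

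Check for D, N: 100% × 1/2 = 50%. The denominator differs in 3 of the 6 pairs and the percentage in 2. These are counts of possible combinations, not probabilities; the documents do not say which occurred.

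**Out-of-specification product (secondary).** Protocol 4.1.1, protocol Table 9-1 and SAP Table 2 treat any treated subject with a DLT as evaluable. Protocol 6.2.1.3 keeps a DLT in a subject given out-of-specification cells out of the tally for a dose level, though it is still reviewed and considered in decisions. Read literally, such a subject is DLT-evaluable yet absent from the tally, and the passages must be reconciled. Counting that event in an overall safety row is not itself an error.

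**The case against.** The strongest case on the other side is that nothing follows from this in practice.

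- **Only two subjects were treated.** The SAP was written with that known, and nothing suggests either was non-evaluable. If both were evaluable, the two denominators coincide. This stands, and it limits the size of the point.
- **No decision uses the row.** There is no hypothesis test. Escalation and the maximum tolerated dose follow the cohort counts in protocol 6.2.1.3, with replacement under 4.1.1. This also stands; the defect concerns reporting.
- **The SAP follows the protocol.** Protocol 9.4 puts safety summaries on the Safety Analysis Set, and an all-treated denominator is legitimate in an adverse event overview. It is therefore not an undisclosed departure. But this row is also the only place where the escalation primary endpoint gets a percentage.
- **Listings fill the gap.** Listings of dosing, follow-up, protocol deviations, laboratory results, vital signs, cell kinetics and disease response would let a reader largely reconstruct evaluability for two subjects. That is a fair mitigation, but no planned output states who was evaluable.
- **The SAP 5 wording could be read as pointing to the DLT Evaluable Set.** SAP 6.5 says all safety analyses and directly governs the row. If the denominator can still be disputed, the SAP should state it.
- **The out-of-specification passages serve different purposes.** Evaluability for analysis and attribution to a dose-level tally can be separate ideas, and no such infusion is documented for either subject. Moving to the DLT Evaluable Set would not by itself reproduce the tally. This is why the matter is only a secondary wording point.

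**Conclusion.** The concern holds and is minor. The SAP's own rules put subjects it calls non-evaluable for DLTs into the denominator of the only DLT percentage, and neither document assigns the DLT Evaluable Set to any analysis. The error can run only toward understatement. With two treated subjects, the worst cases are 50% reported against 100% evaluable, and 0% reported where no rate is estimable. If both subjects were evaluable, there is no numerical effect.

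This rests on reading SAP 6.5 as governing the DLT row in 6.5.1, which is its plain meaning, and on the SAP Table 2 definition that a DLT makes any treated subject evaluable. The actual evaluability of the two subjects is not given.

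**What to change.** In SAP 6.1 and 6.5.1, do one of the following:

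1. State that DLTs are reported as n/N on the DLT Evaluable Set.
2. Keep the row on the Safety Analysis Set and footnote it with the number of DLT-evaluable subjects.

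Either costs one sentence or footnote and needs no new data, because evaluability follows from DLT status, dosing and Day 29 completion.

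For the secondary point, it is enough in the SAP to flag in the DLT listing any subject who received out-of-specification cells, which adds one column. Aligning protocol 4.1.1 and Table 9-1 with 6.2.1.3 would be a separate protocol clarification, and the SAP change does not depend on it.

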6.5.1 Adverse Events

An AE is considered a treatment emergent adverse event (TEAE) if the event started or worsened during the safety reporting period as defined in Section 5.4.

All analyses will be based on TEAE unless otherwise specified. The AE listings will include all AEs (whether treatment-emergent or not).

AEs will be coded using the current version (as of study start) of MedDRA. Severity of AEs will be assessed by the Investigator using the National Cancer Institute (NCI) Common Terminology Criteria for Adverse Events (CTCAE), Version 5.0 toxicity grading criteria except CRS and ICANS, which will be graded by the Investigator according to the ASTCT criteria (1).

An event will be considered treatment related if the investigator considered the event related to the study drug, ie, relationship to NTLA-5001 = “Possible” or “Probable”, or if relationship is missing.

For summaries by System Organ Class (SOC) and preferred term (PT), each subject will be counted once per SOC and once per PT. In the summary of TEAEs by toxicity grade, subjects will be counted once at the highest severity reported at each level of summarization.

A high-level summary of AEs will include the number and percent of subjects with:

- Any TEAEs
- DLTs
- Treatment-related TEAEs
- Serious TEAEs
- Treatment-related serious TEAEs
- Grade ≥ 3 TEAEs
- Grade 3
- Grade 4
- Grade 5
- Treatment-related Grade ≥ 3 TEAEs
- Grade 3
- Grade 4
- Grade 5
- TEAEs leading to study drug infusion interruption
- Treatment-related TEAEs leading to study drug infusion interruption
- TEAEs leading to study drug infusion discontinuation
- Treatment-related TEAEs leading to study drug infusion discontinuation
- Treatment emergent AEs of special interest (AESIs)
- Treatment-related treatment emergent AESIs
- TEAEs leading to death
- Treatment-related TEAEs leading to death

The AESIs are defined in Section 8.5 in the protocol and will be summarized based on the data collected on the “Adverse Events” eCRF.

Adverse Events by Preferred Term

The following summaries will be provided by preferred term only by decreasing frequency.

- TEAEs by PT (all causality)
- Serious TEAEs by PT (all causality)
- Non-serious TEAEs by PT (all causality)

All AE data will be presented in a data listing.

6.5.2 Deaths

Data collected on the “Death” eCRF including date of death and primary cause of death will be presented in a data listing.

6.5.3 Laboratory Data

All laboratory test results will be presented in a data listing sorted by dose level, subject identifier, laboratory test, and date/time of collection. Values outside laboratory normal ranges will be flagged where appropriate. The central laboratory data and local laboratory data will be flagged accordingly.

6.5.4 Vital Signs

All vital sign data will be presented in a data listing.

6.5.5 Electrocardiograms

No electrocardiogram assessment is performed on this study.

6.6 Subgroup Analyses

No subgroup analysis is planned for this study.

6.7 Interim Analysis

No formal interim analysis is planned for this study.

A Data Monitoring Committee (DMC) will be established to perform periodic review of all safety data. Detailed are provided in a DMC Charter.

7 CHANGES TO PROTOCOL PLANNED ANALYSES

Analyses of the following data were planned in the protocol but will not be performed as there were only 2 subjects who received NTLA-5001 when the study was terminated by the Sponsor.

- Overall survival
- Objective response rate
- Composite complete remission rate
- Duration of response
- Event free survival
- Time to progression
- Minimal residual disease
- Analysis of immune parameters and NTLA-5001 cells
- Frequency and persistence of TRAC and TRBC edits
- Gene expression patterns in NTLA-5001 cells
- Translocation rates in NTLA-5001 cells
- Measurement of WT1 expression on AML as assessed by reverse transcription-PCR
- ECOG performance status
- Quality of life as measured by the EORTC QLQ-C30 instrument

The Efficacy Evaluable Set was defined in the protocol and was specified to be used for all disease assessment related efficacy analysis. Disease response assessments will instead be presented in a data listing based on the Safety Analysis Set.

In addition, no summary tables or figures will be created for cell kinetics data. Only a data listing will be created.

8 SUPPORTING DOCUMENTATION

8.1 Appendix 1: List of Abbreviations

Abbreviation	Description
AE(s)	adverse event(s)
AESIs	adverse events of special interest
AML	acute myeloid leukemia
ASTCT	American Society for Transplantation and Cellular Therapy
CRS	cytokine release syndrome
CTCAE	Common Terminology Criteria for Adverse Events
DLT(s)	dose-limiting toxicity(ies)
DMC	Data Monitoring Committee
eCRF	electronic Case Report Form
ECG	electrocardiogram
ECOG	Eastern Cooperative Oncology Group
FAS	full analysis set
GvHD	graft vs host disease
MedDRA	Medical Dictionary for Regulatory Activities
NCI	National Cancer Institute
PK	pharmacokinetic(s)
PT	preferred term
SAE(s)	serious adverse event(s)
SAP	statistical analysis plan
SOC	system organ class
TEAE(s)	treatment-emergent adverse event(s)
WHO	World Health Organization

